### **2.7.2 Deaths**

As mentioned in [Section 2.7.1](#), TEAEs with a fatal outcome will be summarized by SOC and PT.

### **2.7.3 Laboratory data**

Summaries for laboratory values will include observed value, changes and percent changes from ORION-3 baseline at each time point.

A shift analysis using the normal range (except for eGFR and HbA1c) will be done which counts the number of subjects with a low, normal or high value at ORION-3 baseline and a low, normal or high value post baseline.

The following ranges will be used for eGFR and HbA1c:

- For eGFR, the categories will be Severe =  $< 30 \text{ mL/min/1.73m}^2$ ; Moderate =  $\geq 30$  to  $< 60 \text{ mL/min/1.73m}^2$ ; Mild =  $\geq 60$  to  $< 90 \text{ mL/min/1.73m}^2$ ; and Normal =  $\geq 90 \text{ mL/min/1.73m}^2$ .
- For HbA1c, the categories will be  $< 5.7\%$ ,  $\geq 5.7\%$  to  $< 6.5\%$ , and  $\geq 6.5\%$ .

The shift table for the fasting glucose will require the lab sample to be taken while fasting. Samples taken while the subject was not fasting will not be analyzed.

The number and percentage of subjects with potentially clinically significant (PCS) laboratory values and clinically significant (CS) laboratory values (refer to [Appendix 5.4](#) for the criteria) will be summarized by treatment group. HbA1c criteria is explicitly stated in [Appendix 5.4](#). All other PCS and CS criteria are met when both of the following occur:

- Worst post-baseline value meets the thresholds listed in [Appendix 5.4](#)
- Baseline value does not meet the thresholds in [Appendix 5.4](#)

Separate listings of all subjects with PCS and CS laboratory values will be presented. Subjects will appear once per lab parameter but may appear under multiple lab parameters. The worst post-baseline value will be utilized in the analyses.

The number and percentage of subjects satisfying Hy's Law will also be tabulated based on the following lab findings:

- Any elevated post-baseline aminotransferases defined as:
  - $\text{ALT} > 3 \times \text{ULN}$  or
  - $\text{AST} > 3 \times \text{ULN}$
- Elevated post-baseline serum total bilirubin (TBL)  $> 2 \times \text{ULN}$  and serum alkaline phosphatase (ALP) levels  $< 2 \times \text{ULN}$

Subjects must meet all of the criteria listed above at the same time point and have normal lab parameters (ALT, AST, TBL) at baseline to be considered a Hy's Law case. A second summary will be presented that includes subjects who meet all of the criteria listed above at the same time point without regard to the baseline lab parameter results.

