10.3.4.2 Laboratory Tests

Laboratory values will be summarized by treatment group, including changes and percent changes from Baseline (Day 1 of ORION-3) at each time point. Analyses will also be performed for each lab parameter by treatment group for incidence rates of potentially clinical significant values for subjects without potentially clinical significant value at Baseline (Day 1 of ORION-3).

Numerical values of laboratory parameters from different local laboratories with different units and normal ranges will be converted to the conventional units and normalized to a standard set of reference/normal ranges. The normalization process will be performed and separated by each of the laboratory parameters.

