## 2 Statistical methods

### 2.1 Data analysis general information

All analyses will be performed by Novartis or a designated clinical research organization (CRO). The most recent version of SAS available in the statistical programming environment of Novartis or the designated CRO will be used for the analysis.

All study-collected data will be summarized by treatment group using descriptive statistics, graphs, and/or raw data listings. Categorical variables will be summarized using counts and percentages. Percentages are based on the number of subjects in the analysis set for whom there are non-missing data, unless otherwise specified. Continuous variables, including changes from Baseline of ORION-1 or ORION-3, will be summarized using descriptive statistics (n (number of non-missing observations), mean, standard deviation (SD), median, first and third quartiles, minimum and maximum). The precise definitions of the baselines are given in [Table 2-1](#).

Absolute change and percent change from baseline will be calculated as follows:

- Absolute Change from baseline to Day X = Value at Day X – Baseline value.
- Percent Change from baseline to Day X = (Absolute Change/Baseline value)\*100%.

Analyses for the final CSR will be conducted after all participants complete the EOS visit or discontinued early. [REDACTED]

Information regarding DMC analysis will be provided in the DMC charter and a separate DMC SAP/TFL shells.

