## **2.7 Safety analyses**

All safety evaluations will be performed for the following groups unless otherwise specified:

- Subjects on evolocumab from the switching arm (Group 2) for the period between Day 1 (Day 1 of ORION-3) and Day 360.
- Subjects from the inclisiran only arm (Group 1), for the period from Day 1 (Day 1 of ORION-3) until EOS.

█ [REDACTED]

█ [REDACTED]

█ [REDACTED]

All the safety analyses will be performed on the safety population unless otherwise specified. Safety analyses are based on observed values. Any missing safety data including laboratory data will not be imputed.

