## 4 Change to protocol specified analyses

No change from protocol specified analysis was made.

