#### 5.4 Criteria for potentially clinically significant and clinically significant abnormal laboratory tests

Hemoglobin A1c criteria is explicitly stated in the table below.

All other criteria are met when both of the following occur:

- Post-baseline values meet the thresholds below
- Baseline value does not meet the thresholds below

Parameter	Unit	Lower Boundary	Upper Boundary
Hematology			
Hematocrit	%	$\leq 0.8 \times \text{LLN}$	N/A
Hemoglobin	g/dL	$\leq 10 \text{ g/dL}$	N/A
Platelet Count	$10^9/\text{L}$	$\leq 75^*$	$\geq 700^*$
White Blood Cell Count	$10^9/\text{L}$	$\leq 2.8$	$\geq 16$
Serum Chemistry			
Alanine Aminotransferase (ALT/SGPT)	U/L	N/A	$> 1 \text{ and } \leq 3 \times \text{ULN}$
Alanine Aminotransferase (ALT/SGPT)	U/L	N/A	$> 3 \text{ and } \leq 5 \times \text{ULN}^*$
Alanine Aminotransferase (ALT/SGPT)	U/L	N/A	$> 5 \text{ and } \leq 10 \times \text{ULN}^*$
Alanine Aminotransferase (ALT/SGPT)	U/L	N/A	$> 10 \text{ and } \leq 20 \times \text{ULN}^*$
Alanine Aminotransferase (ALT/SGPT)	U/L	N/A	$> 20 \times \text{ULN}^*$
Alkaline Phosphatase	U/L	N/A	$> 2 \times \text{ULN}^*$
Aspartate Aminotransferase (AST/SGOT)	U/L	N/A	$> 1 \text{ and } \leq 3 \times \text{ULN}$

Parameter	Unit	Lower Boundary	Upper Boundary
Aspartate Aminotransferase (AST/SGOT)	U/L	N/A	> 3 and ≤ 5 × ULN*
Aspartate Aminotransferase (AST/SGOT)	U/L	N/A	> 5 and ≤ 10 × ULN*
Aspartate Aminotransferase (AST/SGOT)	U/L	N/A	> 10 and ≤ 20 × ULN*
Aspartate Aminotransferase (AST/SGOT)	U/L	N/A	> 20 × ULN*
Creatine Kinase (CK)	U/L	N/A	> 1 and ≤ 3 × ULN
Creatine Kinase (CK)	U/L	N/A	> 3 and ≤ 5 × ULN
Creatine Kinase (CK)	U/L	N/A	> 5 × and ≤ 10 × ULN*
Creatine Kinase (CK)	U/L	N/A	> 10 and ≤ 20 × ULN*
Creatine Kinase (CK)	U/L	N/A	> 20 × ULN*
Hemoglobin A1C	%	N/A	≥ 6.5% and ≥ 0.5% change from baseline
Serum Creatinine	mg/dL	N/A	≥ 50% increase from baseline or > 2 mg/dL*
Total Bilirubin	mg/dL	N/A	> 2 × ULN*
LLN: Lower limit of the standard reference (normal) range; ULN: Upper limit of the standard reference (normal) range.			
*Clinically significant laboratory boundaries.			

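### For laboratory rows other than HbA1c, the SAP's default denominator keeps subjects already abnormal at baseline, so the PCS/CS percentages are not the incidence the protocol asks for

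*SAP*

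**What the plan says.** **Protocol 10.3.4.2 (Laboratory Tests)** calls for analyses of "incidence rates of potentially clinical significant values for subjects without potentially clinical significant value at Baseline (Day 1 of ORION-3"). This describes incidence in subjects at risk. The protocol does not use a separate clinically significant (CS) label. I read its rule as covering both of the SAP's categories.

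**SAP 2.7.3 (Laboratory data)** reports "The number and percentage of subjects with potentially clinically significant (PCS) laboratory values and clinically significant (CS) laboratory values". Apart from HbA1c, a criterion is met when the worst later value crosses the threshold and, as a second condition, "Baseline value does not meet the thresholds in" Appendix 5.4. The appendix repeats this: "Baseline value does not meet the thresholds below". Neither place names a denominator.

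**SAP 2.1** gives the general rule: "Percentages are based on the number of subjects in the analysis set for whom there are non-missing data, unless otherwise specified". **SAP 2.7** fixes the analysis set: "All the safety analyses will be performed on the safety population unless otherwise specified". That population is everyone dosed, whatever their baseline laboratory status.

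**SAP section 4** states: "No change from protocol specified analysis was made".

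**The concern.** The SAP uses baseline status to decide who counts as a case. The protocol uses it to decide who is at risk. These give the same percentage only when nobody meets the threshold at baseline. Otherwise the SAP's denominator includes people who cannot contribute to that row's numerator, and the printed percentage falls below the protocol's incidence.

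These tables serve the long-term safety objective, and a reader will take the percentages as rates of new abnormality. A programmer who follows the written SAP will not produce the protocol's rate. One who guesses the protocol's intent departs from the written SAP. Section 4 does not alert anyone to the difference.

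**Working it through.** The documents print no figure on this point, so there is nothing to reproduce. The check is a reading of the rules followed by simple algebra.

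**Which denominator the SAP yields**

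1. SAP 2.7.3 and Appendix 5.4 place the baseline condition inside the criterion. It therefore acts on the numerator.
2. Neither section specifies a denominator, so the SAP 2.1 default is not displaced.
3. Under SAP 2.7 the set is the full safety population.
4. The SAP does restrict by baseline status where it means to. In 2.7.4.4 the time-to-diabetes analysis is explicitly limited to subjects free of diabetes at baseline. No such sentence covers the PCS/CS rows.

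**Algebra for one row**

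Let N be the safety subjects with data, f the share already meeting the row's threshold at baseline, and r the incidence among the rest. I take the counted events to be the same under both rules.

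- Events = r × N × (1 − f)
- Protocol rate = events / [N × (1 − f)] = r
- SAP default rate = events / N = r × (1 − f)

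The relative understatement is exactly f.

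**Illustration**

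Protocol Amendment 5 gives 382 enrolled. Protocol 1.2.2 gives the feeder-study allocation as 374 inclisiran and 127 placebo out of 501. Assuming the same split, Group 1 is 382 × 374/501 ≈ 285. Both r = 10% and f are assumptions.

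| f | At-risk N = 285 × (1 − f) | Events = 10% of at-risk N | SAP rate = events / 285 | Protocol rate |
|---|---|---|---|---|
| 0% | 285 | 28.5 | 10.0% | 10.0% |
| 5% | 270.75 | 27.1 | 9.5% | 10.0% |
| 10% | 256.5 | 25.7 | 9.0% | 10.0% |
| 20% | 228 | 22.8 | 8.0% | 10.0% |
| 30% | 199.5 | 20.0 | 7.0% | 10.0% |

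**Where f could be more than trivial**

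- Protocol 4.3 excludes unexplained, confirmed ALT or AST above 2 × ULN and bilirubin above 1.5 × ULN at Study Entry. Read row by row, f should be near zero for the ALT/AST rows above 3 × ULN and for bilirubin above 2 × ULN.
- The same limits leave room in the ALT and AST rows running from 1 to 3 × ULN, and the protocol sets no entry limit on CK. Protocol 1.2.2 also notes that some feeder-study subjects with AST, ALT or CK rises had raised baseline values.

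**Effect on a comparison of columns**

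With equal true risk, the apparent ratio is (1 − f₁)/(1 − f₂). For f of 10% against 20% it is 0.90/0.80 = 1.125. For 20% against 30% it is 0.80/0.70 = 1.14. If f is equal in the two columns, the ratio is 1.

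**The case against.** The strongest reply is that the defect is inferred. No sentence says that baseline-abnormal subjects stay in the denominator, and the table shells are not among the documents. Protocol 10.2.1 carries almost the same default rule, and there it sits alongside the at-risk wording of 10.3.4.2. On this view section 4 of the SAP simply shows that no change was intended, so the protocol's denominator still governs.

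The point about inference stands and limits how firmly this can be put. The rest does not dispose of it. In the protocol, 10.3.4.2 is the specific rule that overrides the default. The SAP has no counterpart, so its own stated rule yields a different rate.

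A reader might also infer four stronger claims that the documents do not support:

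- *That every rate is diluted.* HbA1c has its own criterion, which a subject already at 6.5% or more can still meet. The part of the creatinine criterion that needs a 50% rise cannot be met at baseline. Any row with no baseline cases is unaffected.
- *That a subject abnormal at baseline can never be counted.* If the ALT, AST and CK bands are read row by row, such a subject can still be counted in a higher band. The SAP does not say whether the thresholds to be avoided at baseline are those of the same row or of any row for that parameter. Under the any-row reading, the dilution would extend to the higher bands.
- *That the drug is always favoured.* Absolute percentages are lowered in the evolocumab column as well. A comparison shifts only if f differs between columns, in a direction that cannot be known from the documents. The study is nonrandomized (Protocol 3.6.1).
- *That these tables are the main laboratory evidence.* SAP 2.7.3 also plans shift tables, changes over time and listings. The shift tables show how many subjects started outside the normal range.

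**Conclusion.** The mismatch holds for PCS/CS rows other than HbA1c that have any subject over the threshold at baseline. In those rows, the SAP as written gives the protocol's incidence multiplied by (1 − f), and section 4 does not declare it.

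The algebra is exact, but the size is unknown because the documents give no baseline prevalence. The range of 9.5% to 7.0% in place of 10% rests on the assumed incidence and on an assumed f of 5% to 30%. I would expect little or no effect in the high ALT, AST and bilirubin rows, and a possible effect in the ALT, AST and CK rows from 1 to 3 × ULN, which Appendix 5.4 does not flag as clinically significant. The conclusion also rests on the SAP 2.1 default being applied as written.

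This should be corrected because the SAP departs from the protocol and the repair is cheap. It is not grounds for doubting the safety evaluation as a whole.

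**What to change.** Add to SAP 2.7.3 that, for each row other than HbA1c:

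- the denominator is the safety-population subjects with at least one post-baseline value and a non-missing baseline value that has not reached that row's boundary;
- for the banded ALT, AST and CK rows, this means a baseline at or below the band's lower limit;
- the same baseline condition applies to the numerator;
- each cell prints n/N with the at-risk N.

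The wording for the bands matters. If the rule said only that baseline must fall outside the row, a subject going from 4 × ULN at baseline to a worst later value of 2 × ULN would be counted as a new abnormality in the lowest band, although the value had fallen. The proposed wording also settles whether the baseline condition is applied by row or by parameter.

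If the sponsor prefers the whole-population denominator, section 4 should list it as a change from the protocol. Using the at-risk denominator for the Hy's Law summary that requires normal baseline values is optional. Protocol 10.3.4.2 does not mention that summary, and the SAP already plans a second one that ignores baseline.

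The cost is a short SAP addition and a denominator flag in the laboratory table program, with no new data. The downside is that N varies by row and some percentages become slightly less favourable.

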7.1.6 Clinical Laboratory Assessments

Specimens will be obtained at the time points in the Schedule of Assessments ([Table 6-1](#) and [Table 6-2](#)). Additional aliquots of plasma or serum will be collected at each time point and stored for any clinically indicated efficacy or safety analyses to be conducted at the end of the study.

Subjects will be in a fasted state for all clinical laboratory assessments. Details regarding the processing, shipping, and analysis of samples will be provided in the Laboratory Manual. Note: Efficacy laboratory assessments (eg, LDL-C and PCSK9) are described in [Section 7.2](#).

Laboratory assessments will include:

Hematology – Day 1, Day 360, Day 720, Day 1080 and EOS: hemoglobin, hematocrit, erythrocytes, reticulocytes, platelet counts, mean cell hemoglobin (MCH), mean corpuscular

volume (MCV), mean corpuscular hemoglobin concentration (MCHC), white blood cell count, differential blood count.

Coagulation - Day 1, Day 360, Day 720, Day 1080 and EOS: prothrombin time (PT), international normalized ratio (INR), activated partial thromboplastin (aPTT). Coagulation samples will also be collected at all other visit, however, these samples will be stored for any clinically indicated safety analyses to be conducted at the end of the study.

Chemistry

Blood draws for chemistry will be performed per the Schedule of Assessments (Table 6-1 and Table 6-2). Analysis will vary based on visit day as follows:

- **Full serum chemistry - Day 1, Day 360, Day 720, Day 1080 and EOS**

AST, ALT, alkaline phosphatase (ALP), gamma glutamyl transferase (GGT), total bilirubin (TBIL), uric acid, creatine phosphokinase, albumin, total protein, urea (BUN), creatinine, sodium, potassium, chloride, inorganic phosphate, , direct and indirect bilirubin, , estimated glomerular filtration rate (eGFR), calcium, and bicarbonate.

- Fasting serum glucose and glycated hemoglobin A1C (HbA1C): Days 1, 1080 and EOS only
- High sensitivity C-reactive protein (hsCRP) (fasting): Days 1, 360, 720 and EOS only.

- **Limited serum chemistry all subjects – Days 30, 90, 180, 270, 390, 450, (510 Group 2 only), 540, (570 Group 1 only), 630, 810, (870 Group 1 only), (900 Group 2 only), 990, 1170, 1260, and 1350**

ONLY: AST, ALT, ALP, GGT, TBIL, CPK, creatinine, eGFR, and tryptase (as required).

- Fasting serum glucose and HbA1C: Days 270, 540, 810 and 1350 only

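### Both Hy's Law summaries need the liver criteria met in the same draw, so a bilirubin rise first seen after ALT/AST has fallen to 3 x ULN or below is counted in neither

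*SAP*

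**What the plan says.** SAP 2.7.3 builds the Hy's Law tabulation from two laboratory findings after baseline: ALT or AST above 3 x ULN, and total bilirubin above 2 x ULN with ALP below 2 x ULN. For the first summary, "Subjects must meet all of the criteria listed above at the same time point and have normal lab parameters (ALT, AST, TBL) at baseline". The second covers subjects who "meet all of the criteria listed above at the same time point without regard to the baseline lab parameter results". Only the baseline condition differs between them. No visible text links a transaminase elevation at one draw to a bilirubin elevation at another.

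Protocol 7.1.6 sets the sampling days. The full panel is "Full serum chemistry - Day 1, Day 360, Day 720, Day 1080 and EOS". The limited panel, which still contains AST, ALT, ALP and total bilirubin, is taken on "Days 30, 90, 180, 270, 390, 450, (510 Group 2 only), 540, (570 Group 1 only), 630", then on Days 810, 870 (Group 1), 900 (Group 2), 990, 1170, 1260 and 1350. All Hy's Law components are therefore available at every chemistry draw.

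The SAP also summarises and lists potentially clinically significant and clinically significant laboratory values, one parameter at a time, on the worst post-baseline value (2.7.3, Appendix 5.4).

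**The concern.** A same-draw rule works well when draws are close together, because one of them is likely to catch the overlap. With draws about three months apart, the transaminases can be past their peak before the next sample shows the bilirubin rise.

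A hypothetical subject shows this: ALT 6 x ULN with bilirubin 1.5 x ULN at one draw, then ALT 2.5 x ULN with bilirubin 3 x ULN at the next, ALP normal throughout. Neither draw meets all criteria, so the subject enters neither count, whatever the baseline values were.

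Long-term safety is a secondary objective (protocol 2.2), and protocol 8.4.2 names drug-induced liver injury as an example of a signal for which the sponsor may end the study. The protocol's summary of ORION-1 (1.2.2) relies on the statement that no case met Hy's Law. If the expected count is near zero, a reader will look closely at any single subject, and the planned table would not point to this one.

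**Working it through.** The documents give no figure for this point, so there is nothing to reproduce first.

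**Step 1: gaps between chemistry draws** (protocol 7.1.6, nominal days, EOS = Day 1440).

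- Group 1 days: 1, 30, 90, 180, 270, 360, 390, 450, 540, 570, 630, 720, 810, 870, 990, 1080, 1170, 1260, 1350, 1440. Gaps: 29, 60, 90, 90, 90, 30, 60, 90, 30, 60, 90, 90, 60, 120, 90, 90, 90, 90, 90. The median is 90, and 12 of 19 gaps are 90 days or more. The single 120-day gap is Day 870 to Day 990.
- Group 2 has draws at Days 510 and 900 in place of 570 and 870. The maximum gap is 90 days, in 13 of 19 intervals.
- With the ±7-day windows of Table 6-1, the longest Group 1 gap can reach 120 + 7 + 7 = 134 days. The pandemic window can lengthen it further.

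**Step 2: what the rule needs.** A subject is counted only if some draw falls while both elevations are present (and ALP is below 2 x ULN). If ALT/AST is high for A days from onset and bilirubin starts L days after onset, the overlap lasts A − L days, provided bilirubin stays high at least that long.

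Example: A = 60, L = 45, overlap 60 − 45 = 15 days. Let onset be uniform on Days 1 to 1350, a span of 1349 days. The draws that can fall in the overlap are Days 90 to 1350, which is 17 draws. No gap among them is shorter than 15 days, so the share counted is 17 x 15 / 1349 = 18.9%. For L = 30 the overlap is 30 days: 17 x 30 / 1349 = 37.8%.

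**Step 3: same-draw rule against same-or-next-draw rule.** Simulation on Group 1 nominal days, 400,000 uniform onsets, ALP taken as below 2 x ULN, no repeat tests. The durations are assumptions; the documents give none.

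| ALT/AST high (days) | Bilirubin high (days) | Lag (days) | Same draw | Same or next draw |
|---|---|---|---|---|
| 60 | 60 | 45 | 19% | 45% |
| 90 | 60 | 45 | 54% | 70% |
| 60 | 60 | 30 | 38% | 47% |
| 30 | 30 | 14 | 21% | 23% |
| 90 | 60 | 30 | 71% | 71% |

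Allowing bilirubin at any later draw, instead of only the next one, gives the same percentages in every row. Group 2 behaves much like Group 1. With 60-day elevations and a 40-day lag, on a half-day grid of onsets, the same-draw share is 26% in both groups. The share with both elevations seen at some visit is 47% in Group 1 and 45% in Group 2.

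**Step 4: where the rest of the loss lies.** In the first row, 100 − 45 = 55% of events are missed by either rule, because no suitable draws were taken. An event in that row spans 45 + 60 = 105 days, so it cannot touch both ends of the 120-day interval, and pairing recovers nothing there.

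**Step 5: repeat tests.** Suppose a repeat is drawn every 7 or 14 days after the first scheduled ALT-positive draw until resolution, and all results are analysed (the interval is an assumption). The two rules then agree: 73% and 73% for 60/60 with a 45- or 30-day lag, 40% and 40% for 30/30 with a 14-day lag. In these scenarios the two elevations overlap; if they do not, no amount of repeat sampling puts both in one draw.

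**The case against.** The strongest objection is that the protocol already calls for extra testing. Section 5.3.1 requires abnormal findings to be followed until they resolve or stabilise, and 4.4.2 foresees a repeat liver test at least 4-7 days later. Step 5 shows that such repeats, if analysed, can remove the difference. This stands as a limit on the size of the loss, but not as an answer. Protocol 6.7 keeps unscheduled visits out of the eCRF, and neither document says whether repeat results from the central laboratory enter the analysis dataset.

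A reader might infer that such a case would be invisible, or that one missed case would overturn the safety conclusion. The documents do not support that. ALT/AST above 3 x ULN and bilirubin above 2 x ULN are both clinically significant boundaries in Appendix 5.4, so the subject appears in both sets of listings if baseline was below threshold. A reported liver event enters the hepatic query of Appendix 5.2, and the sponsor and the DMC review safety data during the study. What is missing is an output that joins the two elevations by subject and date.

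A reader might also infer that misses are likely whenever bilirubin follows the transaminases, or that the 120-day gap drives the problem. Neither holds. In the table, the same-draw rule keeps 21/23 = 91% of what the paired rule finds at a 14-day lag, 38/47 = 81% for 60/60 at 30 days, and everything for 90/60 at 30 days. The 120-day gap is one interval of 19 in one group, and the argument is the same at 90 days.

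Finally, the visible text does not define a time point for this rule. Part of the SAP's visit-assignment text is blacked out, so a definition there cannot be excluded.

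**Conclusion.** The point holds as a gap in the tabulation. Both summaries carry the same-draw condition, and a subject with ALT/AST at or below 3 x ULN when bilirubin exceeds 2 x ULN is in neither, unless another draw meets all criteria together. A later bilirubin rise with ALT/AST still above 3 x ULN and ALP below 2 x ULN in that sample is counted as planned.

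The effect ranges from nothing (71% against 71%) to more than a doubling of detected events (19% against 45%). It rests on assumed durations and lags, draws on nominal days, and no analysed repeats. Sparse sampling accounts for many of the misses under either rule, and no table definition can repair that. This is a cheap improvement to a safety display, not a flaw that invalidates the safety analysis.

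**What to change.** Keep the two existing rows in SAP 2.7.3. Add one supportive row, without a baseline restriction: ALT or AST above 3 x ULN at a post-baseline draw, and total bilirubin above 2 x ULN with ALP below 2 x ULN at the same or the next available draw. State that all central-laboratory results are used, including repeats.

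Support it with a subject listing that gives the dates of both draws; ALT, AST, ALP and bilirubin at each; and the baseline values. A plot of peak ALT against peak bilirubin is optional. It would also show a subject whose two elevations are separated by a draw with neither, whom the new row would not count.

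Two details matter. Limiting the pairing to the next draw avoids joining, say, an ALT rise at Day 30 to an unrelated bilirubin rise at Day 1440, and it lost nothing in the scenarios run. Keeping the ALP condition at the bilirubin draw follows the SAP's present construction.

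The cost is one table row, one listing and, if wanted, one figure, from laboratory data already collected. The downside is that a few flagged subjects may not be true cases and will need a line of review.
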